**Table 11. Secondary outcome effect sizes**

	Our previous baseline data	Effect size	Sample size per group
Days in NICU	17.3	3 days	310
Days on ventilator	8.4	2 days	140
Hours on inotropes	81.4	24 hours	179

### f. Analytical Plan

All analysis will be conducted by intention-to-treat analysis. To ensure that randomization has achieved the desired balance, all demographics will be compared

using Fisher's exact or chi-square tests for categorical factors and t tests or non-parametric tests for continuous outcomes. Dichotomous outcomes including the primary outcome will be compared between the hydrocortisone-treated group and control groups while adjusting for NRN center differences using robust Poisson regression, so that adjusted relative risk estimates of the treatment effect can be obtained. For continuous outcomes, non-normally distributed data may be log-transformed prior to analysis. Secondary analyses may be performed adjusting for gestational age or other critical baseline covariates that may be imbalanced across the two treatment groups, in addition to center. Short-term continuous outcomes will be compared between those receiving hydrocortisone and those on placebo using linear regression adjusting for NRN center and other critical baseline covariates that may be imbalanced.

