## 4. Specific Aims

**Goal of study.** Although short term use of hydrocortisone is believed to be safe (see Table 1), evidence is limited to support its use in treating hypotension in the critically ill term and late preterm infant. **Despite this paucity of data, many infants are increasingly receiving glucocorticoids for cardiovascular insufficiency**—13.1% of intubated and mechanically ventilated infants in our own preliminary observational NRN data and 13.5% in a recent report of infants with meconium aspiration syndrome. We propose to **perform a RCT of hydrocortisone** for the treatment of cardiovascular insufficiency in critically ill, term and late preterm newborn infants who are mechanically ventilated in their first 72 postnatal hours. Our

goal is to determine if hydrocortisone treatment improves cardiovascular function, ameliorates other short-term outcomes, and increases survival without neurodevelopmental impairment.

**Specific aims** of this multicenter, randomized, masked, placebo-controlled trial within the NRN are:

- a. Compare the incidence of death or neurodevelopmental impairment at 22-26 months in critically ill, mechanically ventilated, term and late preterm newborn infants receiving inotropes for cardiovascular insufficiency in the first 72 hours of age treated with 7 days of hydrocortisone vs. placebo. We **hypothesize** that hydrocortisone will decrease the incidence of death or neurodevelopmental impairment in these infants compared to placebo.
- b. Compare short-term outcomes between infants treated with hydrocortisone vs. placebo including duration of mechanical ventilation and oxygen therapy, days to full feeding, and length of hospital stay. We **hypothesize** that infants who receive hydrocortisone will spend fewer days on mechanical ventilation and oxygen, will take fewer days to reach full enteral feeds, and will have shorter stays in the hospital.
- c. Compare adverse events (defined below) between infants treated with hydrocortisone vs. placebo. We **hypothesize** that adverse events will not occur at a higher rate in those receiving hydrocortisone compared to placebo.

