## 7. Methods/Procedures

### a. Study Design

The study will be a randomized, multicenter, double-blind, placebo-controlled trial. Patients will be enrolled and randomized in a variable block design, 1:1 ratio of hydrocortisone or placebo.

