### **8. Risks and Benefits**

**Short-term adverse events.** The following will be reported within 72 hours of diagnosis and 24 hours of discovery:

- **Mortality.** No study of hydrocortisone therapy in newborns or in other critically ill populations has shown an increase risk in mortality, and some have shown decreased risk of death. This study population is at high risk of death from the underlying diseases (1.2%–11%).
- **Late-onset ( $\geq 5$  days) culture-confirmed infection.** Recent large randomized controlled trials in adults and preterm newborn infants showed no increased risk of infection from 7–14 days of glucocorticoid treatment. However, culture-proven late onset infection will be tracked and reported. Early and late onset culture-proven infection in this population is 1.4% and 4.2% respectively (Vermont Oxford Network 2009). Anticipated incidence <4.2%.
- **Gastrointestinal perforation.** In contrast to the extremely low birth weight infant where the incidence of spontaneous intestinal perforation is 4%, this patient population is

developmentally more mature and should not be at risk for this event, particularly since these patients will not be simultaneously exposed to indomethacin.

- **Hypertension.** These infants are often on inotropes, which often cause high blood pressure by themselves. Glucocorticoids' actions are to increase blood pressure. It is unknown if the combination of these two therapies results in a higher occurrence of hypertension. This will be tracked by counting the number of 12-hour periods in which the blood pressure was higher than 95th percentile for weight and age and the receipt of any antihypertensive medication. Incidence is unknown.
- **Hyperglycemia.** Higher dose glucocorticoids can raise blood glucose levels acutely and for short periods of time (hours), without long-term consequences. No study to date has shown a need for insulin secondary to glucocorticoid administration for the treatment of hypotension. Data on the use of insulin will be collected if administered during the study drug time and when glucose is >180mg/dl on at least two determinations at least 6 hours apart. Anticipated incidence <1%.

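### The analysis plan has no rule for a dichotomous outcome with no events in one arm, where its center-adjusted robust Poisson test is invalid; this is foreseeable for rare adverse events

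*Combined protocol and SAP*

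**What the plan says.** Section 7.f (Analytical Plan) names one model for binary endpoints: "Dichotomous outcomes including the primary outcome will be compared between the hydrocortisone-treated group and control groups while adjusting for NRN center differences". The stated way of doing this, and the reason for choosing it, is "using robust Poisson regression, so that adjusted relative risk estimates of the treatment effect can be obtained". It does not say what happens when events are sparse or one arm has none. Fisher's test appears only in the sentence on baseline balance, which calls for "exact or chi-square tests for categorical factors and t tests or non-parametric tests for continuous outcomes".

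Aim c in section 4 is to "Compare adverse events (defined below) between infants treated with hydrocortisone vs. placebo". No separate method is given for that final comparison. The DSMC section covers only interim looks at death and at a composite of serious adverse events.

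Section 8 (Risks and Benefits) expects some of these events to be very rare. On gastrointestinal perforation it describes the population as "developmentally more mature and should not be at risk for this event". On insulin it says "No study to date has shown a need for insulin secondary to glucocorticoid administration for the treatment of hypotension", and the same hyperglycemia item ends with "Anticipated incidence <1" percent.

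**The concern.** Robust Poisson regression works well for common binary outcomes. It fails when one arm has no events: the estimated log relative risk has no finite value, yet the sandwich standard error stays finite. A Wald test built from the two can then return a minute p-value from a single event.

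The outcomes most exposed are the rare steroid-related harms that aim c is meant to assess. The error runs both ways: 1 vs 0 can look like proven harm and 0 vs 1 like proven protection. If the analyst sees the problem and substitutes another test, that choice is made after the split by arm is known, which prespecification is meant to prevent.

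**Working it through.** **Inputs.** Total enrollment is 646 (section 7.e). Allocation is "1:1 ratio of hydrocortisone or placebo" (section 7.a), so 646 / 2 = 323 per arm. No loss is deducted, on the assumption that in-hospital events are known for all infants. The documents' only figure for these rare events is below 1%, attached to the hyperglycemia/insulin item. No perforation rate is given for this population, so 0.1% to 1% is an assumed range. The trial's number of centers is not stated; 16 is assumed, from the earlier observational study in section 6b.

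**The plan's own figure.** For 30% vs 20%, two-sided 5% and 80% power, the standard two-proportion formula gives 294 per arm, 588 in total. 588 x 1.10 = 646.8, in line with 646. The documents give no sparse-event figure to reproduce.

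**Step 1: how likely is one empty arm?** With a common event rate r, one arm is empty with probability q = (1 - r)^323. Exactly one arm is empty with probability 2q(1 - q).

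| r | q | 2q(1 - q) |
|---|---|---|
| 0.1% (assumed) | 0.724 | 40% |
| 0.2% (assumed) | 0.524 | 50% |
| 0.3% (assumed) | 0.379 | 47% |
| 0.5% (assumed) | 0.198 | 32% |
| 1% (upper limit of the stated figure) | 0.039 | 7.5% |

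**Step 2: why the test fails.** Take a events in one arm, none in the other, n = 323 per arm, no center terms.
- Arm with events: fitted rate a/n, sandwich variance of the log rate 1/a - 1/n.
- Empty arm: the fitted rate m tends to 0. Its sandwich variance is n m² / (n m)² = 1/n, which stays finite.
- The sum is 1/a, so SE = 1/√a. It is 1.00 for one event and 0.71 for two.
- The log relative risk has no maximum and grows by about 1 per Newton step.

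The p-value therefore reflects when the software stops. For 1 vs 0 it is 1e-8 after 5 steps, 1e-26 after 10 and 4e-95 after 20. A standard fit with default settings reports convergence with log relative risk 20.4, SE 0.998 and p = 1e-92. The model-based SE on the same data gives p = 0.999.

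| Split | Robust Poisson p, no center terms | Fisher p |
|---|---|---|
| 1 vs 0 | 1e-92 | 1.00 |
| 2 vs 0 | 7e-184 | 0.50 |
| 3 vs 0 | 4e-303 | 0.25 |

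**Step 3: adding the prescribed center terms.** With 16 center effects and the treatment coefficient profiled, 1 vs 0 gives 2e-4 after 3 steps, 7e-9 after 5 and 3e-27 after 10. Default fits gave very small p-values at 1 vs 0, from 2e-22 to about 1e-93. At 2 vs 0 and 3 vs 0, results ran from 2e-6 to clearly non-significant (0.27 and 0.39) or an undefined SE, depending on how events fell across centers.

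**Step 4: false-positive rate with no true effect.** Four sets of simulated trials with center adjustment, the largest with 3,000 trials per rate, gave:

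| True rate | Robust Poisson rejects | Fisher rejects (3,000-trial set) |
|---|---|---|
| 0.3% | 40-46% | 0.07% |
| 0.5% | 24-36% | 0.3% |
| 1% | 6-9% | 1.3% |

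The spread reflects simulation error and how each fit handles breakdown.

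**Step 5: where the problem stops.** With at least one event per arm the test is not extreme, even without center terms: 2 vs 1 gives p = 0.57 and 5 vs 1 gives 0.14. In the 3,000-trial set at 1%, rejections were 8.0% in total, of which 7.4% came from tables with an empty arm. The other tables contributed 0.6%. At 2% and above, simulated rejection was 3-5%.

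**The case against.** Four points on the other side carry weight.

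**Scope.** Perforation, insulin use, hyperglycemia and hypertension are not in Tables 8 or 9, where items are labeled dichotomous. A reader might infer that section 7.f expressly prescribes this model for every adverse event. It does not; that is an inference from aim c and the absence of any other method. On the narrower reading, the final comparison under aim c has no stated method, so the same sentence is still needed. NEC stage II or greater is in Table 9 and falls under 7.f on any reading, though its expected rate is not stated.

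**Certainty of the output.** A reader might infer that splits of 1-0, 2-0 and 3-0 would all be reported as overwhelming evidence. The most extreme p-values come from fits without the center terms that the plan requires. With them, 2-0 and 3-0 can give unremarkable or undefined results. Those are numerical breakdown and do not make the test valid, but they rule out the stronger claim.

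**Visibility.** A relative risk of several hundred million would probably be noticed. That makes a false report less likely, but leaves the replacement test to be chosen after the data are seen.

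**Reach.** Late-onset infection (anticipated below 4.2%) and death (1.2% to 11%) will rarely have an empty arm, and the interim rules use death and a composite. This stands, and it limits the point mainly to perforation and insulin use.

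**Conclusion.** The gap is real and should be fixed, but it does not threaten the trial's main conclusion. When exactly one arm has no events, the relative risk that section 7.f seeks does not exist and the robust Wald test is invalid. At the stated ceiling of 1% this happens by chance in 7.5% of comparisons, and the false-positive rate is only modestly above nominal (6-9%). The larger figures, 32% and 47% for an empty arm and about 24-46% for false positives, rest on assumed rates of 0.5% and 0.3%. They also assume 323 per arm with complete in-hospital data and, for the false-positive rates, 16 centers.

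A reader might infer that the primary analysis or the sample size is affected. Neither is: the primary outcome is planned at 20-30% events, where robust Poisson is sound. The interim rules and common secondary outcomes are also untouched.

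**What to change.** Add one sentence to section 7.f: for any dichotomous outcome or adverse event with no events in one arm, or for which the robust Poisson model gives no finite estimate, the arms will be compared with an exact test, and the risk difference reported with an exact confidence interval. Name the test in advance, either a center-stratified exact test or Fisher's exact test. State that the rule covers the aim c adverse events, which also settles their final-analysis method. Keep robust Poisson everywhere else.

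An empty-arm trigger is enough on these calculations. At 1%, the 0.6% of rejections from other tables plus at most Fisher's 1.3% gives no more than 1.9%. A wider trigger based on a minimum total number of events is not needed on this evidence.

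The cost is one sentence and slightly conservative tests: at 323 per arm, Fisher needs 6 vs 0 to fall below 5% (p = 0.031; 5 vs 0 gives 0.062). Sample size, primary analysis and trial conduct do not change.

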### c. Study Intervention

**Randomization criterion. Decision of the clinical care team to treat with** an inotrope (dopamine, dobutamine, epinephrine, or norepinephrine) within the first 72 hours of life, at a minimum dose of 5 mcg/kg/min (epinephrine 0.01 mcg/kg/min), will be the trigger for randomization to study drug. Blood pressure will **not** be a criterion for randomization. Low dose dopamine (<5mcg/kg/min) initiated for low urine output does not qualify for randomization. Low blood pressure did not correlate with interventions for cardiovascular insufficiency in our multicenter NRN observational study (see section 6b, *Preliminary Studies, above*). However, receipt of inotrope support was associated with significantly worse outcomes, including a mortality rate of almost 16% vs. 4%. Therefore, this is a reasonable clinical indicator of adverse outcomes.

**Randomization method.** Randomization will be stratified by Network center using a randomly permuted block randomization algorithm devised by the NRN Data Coordinating Center at RTI. A centralized secure, password-protected web-based (Hatteras Clinical DMS) randomization process will be used to allocate infants to either hydrocortisone or placebo. The medication will be reconstituted by the pharmacist, and caregivers will remain blinded. Placebo will be normal saline and will be given in equal volume to a hydrocortisone dose and delivered at same rate.

**Study Drug.** Enrolled infants who receive inotrope therapy before 72 hours postnatal age **will be randomized to receive 7 days of hydrocortisone** (hydrocortisone sodium succinate, plain; will not have benzyl alcohol) given through intravenous line, po if no line or by intramuscular injection (I.M.) (if no intravenous line and infant is NPO) **or 7 days of intravenous, po or I.M. placebo** (normal saline in equal volume). Hydrocortisone dosing will be 2.5 mg/kg/day on day 1, 2 mg/kg/day on days 2 and 3, 1 mg/kg/day on days 4 and 5, then 0.5 mg/kg/day on days 6 and 7.

- 1 mg/kg loading dose x 1
- 0.5 mg/kg q 6 hours x 12 doses
- 0.5 mg/kg q 12 hours x 4 doses
- 0.5 mg/kg q day x 1 dose

We will continue hydrocortisone for 7 days, weaning after the first 3 days, to avoid possible rebound hypotension and in consideration of possible down-regulation of glucocorticoid

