### e. Sample Size Estimate

Determining a sample size based on available data is limited by the available studies on long-term outcomes including neurodevelopmental impairments or death in term and late preterm infants who have cardiovascular instability and require cardiovascular support. This sample size is based on the best available data, which is closest to the population proposed to study. Based on previous data, the incidence of death or any neurodevelopmental impairment (permanent hearing loss, blindness, moderate or severe cerebral palsy or Bayley MDI or PDI scores <70) was 32% in a similar population of critically ill newborn infants with respiratory distress and in need of mechanical ventilation, but excluding congenital diaphragmatic hernia defects. Based on 4 additional studies in similar populations of term and late preterm infants with respiratory failure, the average incidence of death or any neurodevelopmental impairment was 30%. If these studies had all included mild impairment the event rate would have been higher.

The trial is powered at 80% to detect a reduction in the primary outcome of death or any neurodevelopmental impairment at 22-26 months from 30% to 20%, for a relative risk reduction of 33%, and a relative risk of 0.67, using a two tailed test with 5% Type I error. Allowing for 10% attrition, the required sample size for this scenario is 646 (Table 10). This sample size will also provide >80% power to detect treatment differences in important secondary outcomes of days in the NICU, intubated and on a ventilator and hours on inotropes without adjusting for multiple comparisons (Table 11)."

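### The main model for the short-term continuous outcomes takes unnamed covariates because they look imbalanced, which leaves the model open and forgoes the precision that a fixed prognostic set would give

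*Combined protocol and SAP*

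**What the plan says.** Section 7.f (Analytical Plan) sets three rules.

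- Dichotomous outcomes, including the primary, are compared by robust Poisson regression adjusted for center. That model is fixed, and center is also the stratification factor: "Randomization will be stratified by Network center" (section 7.c).
- Secondary analyses may adjust further, for gestational age or for other critical baseline covariates that prove imbalanced. These are optional.
- Short-term continuous outcomes are compared "using linear regression adjusting for NRN center and other critical baseline covariates that may be imbalanced". This is the only model given for them.

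The same section opens with baseline testing between the arms: "To ensure that randomization has achieved the desired balance, all demographics will be compared", with Fisher, chi-square, t or non-parametric tests. The number of tests and the threshold are not given. The protocol nowhere lists covariates chosen because they predict outcome.

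**The concern.** In a correctly randomized trial a baseline difference between arms is a chance event, and testing it says nothing about whether the variable matters for the outcome. A small imbalance in a strong predictor can move the estimate more than a significant imbalance in a weak one. Adjustment pays when the covariate predicts the outcome, whether or not it is balanced.

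Here imbalance is the criterion in the main model, not in a sensitivity analysis. Two analysts following section 7.f could fit different models to the same data, and neither could have written the model down in advance. The outcomes affected are those of Specific Aim b. Gestational age is not controlled by design, because randomization is stratified by center only, and the third rule does not guarantee that it enters the model.

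**Working it through.** **1. The plan's own sample size.** Inputs from section 7.e: 30% against 20%, 80% power, "using a two tailed test with 5% Type I error", 10% attrition; equal allocation from section 7.a. With unpooled variance, n per arm = (1.960 + 0.842)² × (0.30×0.70 + 0.20×0.80) / 0.10² = 290.4. Then 2 × 290.4 / 0.9 = 645.4, which rounds up to the stated 646. The figure reproduces. It concerns the primary outcome, whose model is fixed, so nothing below changes it.

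**2. How often chance alone flags a covariate.** Assume k independent tests at 5%. P(at least one flagged) = 1 − 0.95^k: 23% for k = 5, 40% for 10, 54% for 15, 64% for 20. If three of ten candidates are truly prognostic, the chance that any of those three is flagged is 1 − 0.95³ = 14%.

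**3. What prognostic adjustment is worth.** In a linear model, covariates explaining a share R² of the outcome variance multiply the standard error by √(1 − R²), and the gain equals a sample larger by the factor 1/(1 − R²). The documents give no R², so 0.10 to 0.20 is an assumption: 1/0.90 = 1.11 and 1/0.80 = 1.25, or 11-25% more infants.

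**4. Applied to days in NICU.** Table 11 gives a 3-day difference and 310 per group but no SD. Assuming that 310 corresponds to 80% power, the implied SD is 3 × √(310/2) / 2.802 = 13.3 days.

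| Assumed R² | SE ratio | n per group for 80% power | Power at 310 per group |
|---|---|---|---|
| 0 | 1.00 | 310 | 80% |
| 0.10 | 0.95 | 279 | 84% |
| 0.20 | 0.89 | 248 | 88% |
| 0.30 | 0.84 | 218 | 92% |

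**5. Selection against pre-specification.** A simulation used 310 per arm, ten independent candidate covariates (three prognostic), balance tests at 5%, normal outcomes and 4,000 runs per scenario. Center effects were not modelled, so the no-covariate model stands in for center only.

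| | R² 0.10 | R² 0.20 | R² 0.30 |
|---|---|---|---|
| Mean SE (SD units), no covariates | 0.080 | 0.080 | 0.080 |
| Mean SE, imbalance-selected | 0.080 | 0.080 | 0.080 |
| Mean SE, pre-specified prognostic | 0.076 | 0.072 | 0.067 |
| Power, no covariates | 80% | 80% | 81% |
| Power, imbalance-selected | 81% | 81% | 82% |
| Power, pre-specified prognostic | 84% | 88% | 92% |
| Type I error, imbalance-selected | 4.8% | 4.2% | 4.4% |

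Some covariate was selected in about 40% of runs and a prognostic one in about 14-15%, as step 2 predicts.

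**6. Evidence on gestational age.** Table 6-2 gives medians for inotrope-treated infants on either side of 37 weeks.

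| Outcome | Below 37 weeks | 37 weeks or more |
|---|---|---|
| Day of full nipple feeding | 20.5 | 14 |
| Days on ventilator | 7 | 9.5 |
| Days on oxygen | 10.5 | 11 |
| Days in NICU | 16 | 17 |

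Gestational age separates feeding and, less strongly, ventilation. It hardly separates oxygen days or NICU days. The feeding definition also differs from the trial's (nipple feeding here, enteral volume in Table 9), so that row is only indicative.

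**The case against.** The strongest reply is that little harm is shown.

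- **Precision.** Against a center-only model, imbalance selection costs nothing: the mean SE is 0.080 either way. This stands. The loss is only relative to pre-specified prognostic adjustment.
- **Validity.** A reader might infer that p-values and intervals for these outcomes are invalid because of the selection step. The simulation does not support that under a mechanical 5% rule: type I error was 4.2-4.8%. It did not model open discretion after outcomes are seen, which section 7.f also leaves possible.
- **Mechanism.** A reader might infer that the baseline tests choose the covariates. The section places the two side by side but never says so. It is a reasonable inference, not a stated rule. *Critical* may also have been meant as prognostic, and gestational age is named for the optional analyses. Even so, the sentence for continuous outcomes still makes imbalance the condition and gives no list.
- **Size.** Table 6-2 gives little support for gestational age alone explaining 10-20% of the variance in NICU days. This stands, and it is why a severity measure belongs in the set. On the same 80% assumption, the Table 11 counts for ventilator days (140) and inotrope hours (179) imply about 99% and 96% power at 323 randomized per arm (646/2), so extra precision matters less there.

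Two further inferences fail. The primary result is not data-driven, since its model is fixed. The higher mortality below 37 weeks in Table 6-2 (14.3% against 9.8%) does not bear on this point either, because death is dichotomous and goes to the center-only model.

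**Conclusion.** The point holds for the short-term continuous outcomes only. Their main model is not fixed in advance and its covariates are described by chance imbalance, with no list, no threshold and no definition of critical. The consequences are open analyst discretion and forgone precision, not a demonstrated error-rate problem.

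The size is 11-25% in effective sample, or 80% rising to about 84-88% power for days in NICU at 310 per group. This rests on an assumed R² of 0.10-0.20, on an SD back-solved from Table 11 at 80% power, and on a normal linear model. The gain will differ by outcome and may be small where neither gestational age nor severity predicts much. The margin for days in NICU is thin (310 needed, 323 randomized per arm), so it is the outcome in Table 11 with most to gain from any added precision. This is worth correcting but does not threaten the trial's main conclusion.

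**What to change.** In section 7.f, before unblinding:

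1. Fix the covariates for all continuous-outcome models as center, gestational age and one pre-dose severity measure, used whatever the observed balance.
2. Choose a severity measure that the protocol already records before study drug. Section 7.c records concurrent medications just before study drug, including inotropes. Table 8 has blood pressure, heart rate and fluid boluses from before study drug. Because starting an inotrope triggers randomization, inotrope use as yes/no would hardly vary, so the number of agents would be more informative. Oxygenation index or respiratory severity score should be named only if a pre-dose value is confirmed, since section 7.d lists both as outcomes and states no pre-dose measurement.
3. Use the same set in the optional secondary adjusted analysis of the primary outcome. Leave the center-only primary analysis as it is.
4. Keep the baseline comparison descriptive, or at least state that its tests do not choose covariates.

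The cost is a few sentences, with no added enrolment and no new data if a recorded measure is chosen. The small downside is that a rule is needed for infants whose baseline severity value is missing.
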